11. DRUG INFORMATION

11.1 Nivolumab

Nivolumab is a human monoclonal antibody that blocks the interaction between PD-1 and its ligands, PD-L1 and PD-L2. Nivolumab is an IgG4 kappa immunoglobulin that has a calculated molecular mass of 146 kDa.

Bristol-Myers Squibb (BMS) will supply nivolumab. Ordering of nivolumab will take place through BMS. Each participating institution will receive its own supply of drug.

11.1.1 Pharmacokinetics (PK)

Nivolumab as a single agent: A pooled analysis dataset from a comprehensive population pharmacokinetics analysis dataset consisting of covariate data from 3203 patients with melanoma (n = 875), RCC (n = 695), non-small cell lung cancer (n = 896), squamous cell carcinoma of the head and neck (n = 172), classical Hodgkin's Lymphoma (n = 256), and urothelial carcinoma (n = 308) was used to simulate exposures from nivolumab clinical trials. Using a previously established population pharmacokinetics model across multiple tumor types, nivolumab exposure was predicted for 480 mg every 4 weeks and 3 mg/kg every 2 weeks dose schedules.

The time-averaged concentration over the first 28 days for nivolumab 480 mg every 4 weeks was 27% higher compared to nivolumab 3 mg/kg every 2 weeks. The time-averaged concentration at steady-state was similar between these two dosing schedules.

To analyze exposure-response safety, a pooled safety dataset from nivolumab clinical trials containing 2560 patients with melanoma (n = 481), RCC (n = 604), squamous non-small cell lung cancer (n = 293), non-squamous non-small cell lung cancer (n = 354), squamous cell carcinoma of the head and neck (n = 172), classical Hodgkin's Lymphoma (n = 253), and urothelial carcinoma (n = 308), who received nivolumab 1 to 10 mg/kg every 2 weeks or 0.3 to 10 mg/kg every 3 weeks were used. Logistic regression models were used to describe the relationships between nivolumab exposure and the risk of AEs (AEs leading to discontinuation or death, AEs > Grade 3, immune mediated AEs > Grade 2). Cavgd28 was the designated exposure measure for exposure-response safety analysis. Exposure (C_{max}) produced by nivolumab 480 mg every 4 weeks was lower than that produced by 10 mg/kg every 2 weeks, which has been shown to have a favorable safety and tolerability profile. The predicted risk of experiencing AEs leading to discontinuation or death was similar between the 480 mg every 4 weeks and 3 mg/kg every 2 weeks dosing schedules across the tumor types.

To analyze exposure-response efficacy, individual datasets from nivolumab clinical trials of patients with melanoma (n = 364), RCC (n = 604), squamous non-small cell lung cancer (n = 293), and non-squamous non-small cell lung cancer (n = 354), who received nivolumab 1 to 10 mg/kg every 2 weeks or 0.3 to 10 mg/kg every 3 weeks were used. OS was assessed by Cox Proportional Hazards and objective response by logistic regression. The predicted OS for the 480 mg every 4 week dose was similar to the 3 mg/kg every 2 week dose in the four indications. In predicted probabilities of achieving response, there were no differences between the 480 mg every 4 week dose and 3 mg/kg every 2 week dose, consistent with previously established flat exposure-efficacy relationships.

Nivolumab in combination with ipilimumab: The geometric mean (%CV) CL, V_{ss}, and terminal half-life of nivolumab were 10.0 mL/h (50.3%), 7.92 L (30.1%), and 24.8 days (94.3%), respectively. When administered in combination, the CL of nivolumab was increased by 24%, whereas there was no effect on the clearance of ipilimumab. When administered in combination, the clearance of nivolumab increased by 42% in the presence of anti-nivolumab antibodies.

There was no effect of anti-ipilimumab antibodies on the clearance of ipilimumab.

Specific Populations: Based on a population PK analysis, the clearance of nivolumab increased with increasing body weight supporting a weight-based dose. The population PK analysis suggested that the following factors had no clinically important effect on the clearance of nivolumab: age (29 to 87 years), gender, race, baseline LDH, PD-L1 expression, tumor type, tumor size, renal impairment, and mild hepatic impairment.

Renal Impairment: The effect of renal impairment on the clearance of nivolumab was evaluated by a population PK analysis in subjects with mild (eGFR 60 to 89 mL/min/1.73 m²; n=313), moderate (eGFR 30 to 59 mL/min/1.73 m²; n=140), or severe (eGFR 15 to 29 mL/min/1.73 m²; n=3) renal impairment. No clinically important differences in the clearance of nivolumab were found between subjects with renal impairment and subjects with normal renal function.

Hepatic Impairment: The effect of hepatic impairment on the clearance of nivolumab was evaluated by population PK analyses in subjects with mild hepatic impairment (total bilirubin ≤ ULN and AST > ULN or total bilirubin < 1-1.5 x ULN and any AST; n=92). No clinically important differences in the clearance of nivolumab were found between subjects with mild hepatic impairment and subjects with normal hepatic function. Nivolumab has not been studied in subjects with moderate (total bilirubin > 1.5-3 x ULN and any AST) or severe hepatic impairment (total bilirubin > 3 x ULN and any AST).

11.1.2 Preparation

Nivolumab is a sterile, preservative-free, non-pyrogenic, clear to opalescent, colorless to pale yellow liquid that may contain light (few) particles. Nivolumab injection for IV infusion is supplied in single-use vials. Each mL of Nivolumab solution contains nivolumab 10 mg, mannitol (30 mg), pentetic acid (0.008 mg), polysorbate 80 (0.2 mg), sodium chloride (2.92 mg), sodium citrate dihydrate (5.88 mg), and Water for Injection, USP. May contain hydrochloric acid and/or sodium hydroxide to adjust pH to 6.

Injection: 100 mg/10 mL (10 mg/mL) solution in a single-use vial.

Visually inspect drug product solution for particulate matter and discoloration prior to administration. Nivolumab is a clear to opalescent, colorless to pale-yellow solution. Discard the vial if the solution is cloudy, discolored, or contains extraneous particulate matter other than a few translucent-to-white, proteinaceous particles. Do not shake the vial.

Withdraw the required volume of nivolumab and transfer into an intravenous container. Dilute nivolumab with either 0.9% Sodium Chloride solution or 5% Dextrose solution to prepare an infusion with a final concentration ranging from 1 mg/mL to 10 mg/mL. Mix diluted solution by gentle inversion. Do not shake. Discard partially used vials or empty vials of nivolumab.

11.1.3 Storage and Stability

The product does not contain a preservative. Store nivolumab under refrigeration at 2°C to 8°C (36°F-46°F). Protect nivolumab from light by storing in the original package until time of use. Do not freeze or shake.

After preparation of infusion, store the nivolumab infusion either:

- at room temperature for no more than 8 hours from the time of preparation. This includes room temperature storage of the infusion in the IV container and time for administration of the infusion or
- under refrigeration at 2°C to 8°C (36°F to 46°F) for no more than 24 hours from the time of infusion preparation.
- Do not freeze.

11.1.4 Administration

Administer the infusion over approximately 30-minutes through an IV line containing a sterile, non-pyrogenic, low protein binding in-line filter (pore size of 0.2 micrometer to 1.2 micrometer).

Do not coadminister other drugs through the same intravenous line. Flush the intravenous line at end of infusion. When administered in combination with ipilimumab, infuse nivolumab first followed by ipilimumab on the same day. Use separate infusion bags and filters for each infusion.

11.1.5 Handling and Disposal

Accountability for investigational product is the responsibility of the investigator. The research pharmacy will maintain a careful record of the inventory and disposition of the agent using the NCI Drug Accountability Record Form (DARF) or another comparable drug accountability form.

Qualified personnel, familiar with procedures that minimize undue exposure to themselves and the environment, should undertake the preparation, handling, and safe disposal of the chemotherapeutic agent in a self-contained and protective environment.

Drug should be destroyed at the site, after the investigator approves the drug destruction policy at the site. Drug will not be returned to BMS. Destruction will be documented in the Drug Accountability Record Form.

11.1.6 Compatibility

No incompatibilities between the nivolumab and ipilimumab have been observed. When both study drugs are to be administered on the same day, separate infusion bags and filters must be used for each infusion. Nivolumab is to be administered first. The nivolumab infusion must be promptly followed by a saline flush to clear the line of nivolumab before starting the ipilimumab infusion. The second infusion will always be ipilimumab, and will start at least 30 minutes after completion of the nivolumab infusion.

Ipilimumab may be diluted in 0.9% Sodium Chloride Solution or 5% Dextrose solution. Nivolumab may be diluted in 0.9% Sodium Chloride Solution.

11.1.7 Adverse Events

Based on data from phase II and III studies in RCC, nivolumab monotherapy has an acceptable safety profile. Based on data from phase III study of nivolumab versus everolimus in RCC, treatment-related AEs of any grade occurred in 319 of the 406 subjects (79%) treated with nivolumab. The most common treatment-related AEs among subjects who received nivolumab were fatigue (134 subjects, 33%), nausea (57 subjects, 14%), and pruritus (57 subjects, 14%).

Grade 3 or 4 treatment-related AEs occurred in 76 of the 406 subjects (19%) treated with nivolumab. The most common grade 3 or grade 4 event was fatigue (10 subjects, 2%) with nivolumab. Treatment-related AEs leading to treatment discontinuation occurred in 31 of the 406 subjects (8%) treated with nivolumab. No deaths from study-drug toxic effects were reported in the nivolumab group. Please refer to the most current IB and package insert for a comprehensive list of AEs.

11.2 Ipilimumab

Ipilimumab is a recombinant, human monoclonal antibody that binds to the CTLA-4. Ipilimumab is an IgG1 kappa immunoglobulin with an approximate molecular weight of 148 kDa. Ipilimumab is produced in mammalian (Chinese hamster ovary) cell culture.

Bristol-Myers Squibb (BMS) will supply ipilimumab. Ordering of ipilimumab will take place through BMS.

11.2.1 Pharmacokinetics (PK):

Ipilimumab as a single agent: The pharmacokinetics of ipilimumab was studied in 499 subjects with unresectable or metastatic melanoma who received doses of 0.3, 3, or 10 mg/kg administered once every 3 weeks for four doses. Peak concentration (C_{max}), trough concentration (C_{min}), and area under the curve (AUC) of ipilimumab were found to be dose proportional within the dose range examined. Upon repeated dosing of ipilimumab

administered every 3 weeks, ipilimumab clearance was found to be time invariant, and minimal systemic accumulation was observed as evident by an accumulation index of 1.5-fold or less. Ipilimumab steady-state concentration was reached by the third dose. The following mean (percent coefficient of variation) parameters were generated through population PK analysis: terminal half-life of 14.7 days (30.1%); systemic clearance (CL) of 15.3 mL/h (38.5%); and volume of distribution at steady-state (V_{ss}) of 7.21 L (10.5%). The mean (\pm SD) ipilimumab C_{min} achieved at steady-state with the 3-mg/kg regimen was 21.8 mcg/mL (\pm 11.2).

Nivolumab in combination with ipilimumab: The geometric mean (%CV) CL, V_{ss}, and terminal half-life of nivolumab were 10.0 mL/h (50.3%), 7.92 L (30.1%), and 24.8 days (94.3%), respectively. When administered in combination, the CL of nivolumab was increased by 24%, whereas there was no effect on the clearance of ipilimumab. When administered in combination, the clearance of nivolumab increased by 42% in the presence of anti-nivolumab antibodies.

There was no effect of anti-ipilimumab antibodies on the clearance of ipilimumab.

Specific Populations: Cross-study analyses were performed on data from subjects with a variety of conditions, including 420 subjects with melanoma who received single or multiple infusions of ipilimumab at doses of 0.3, 3, or 10 mg/kg. The effects of various covariates on ipilimumab PKs were assessed in population pharmacokinetic analyses.

Ipilimumab CL increased with increasing body weight; however, no dose adjustment of Ipilimumab is required for body weight after administration on a mg/kg basis. The following factors had no clinically meaningful effect on the CL of ipilimumab: age (range 26 to 86 years), gender, concomitant use of budesonide, performance status, HLA-A2*0201 status, positive anti- ipilimumab antibody status, prior use of systemic anticancer therapy, or baseline lactate dehydrogenase (LDH) levels. The effect of race was not examined as there were insufficient numbers of subjects in non-Caucasian ethnic groups.

Renal Impairment: Creatinine clearance at baseline did not have a clinically important effect on ipilimumab pharmacokinetics in subjects with calculated creatinine clearance values of 29 mL/min or greater.

Hepatic Impairment: Baseline AST, total bilirubin, and ALT levels did not have a clinically important effect on ipilimumab pharmacokinetics in subjects with various degrees of hepatic impairment.

11.2.2 Preparation

Ipilimumab is a sterile, preservative-free, clear to slightly opalescent, colorless to pale yellow solution for intravenous infusion, which may contain a small amount of visible translucent-to- white, amorphous ipilimumab particulates. It is supplied in single-use vials of 200 mg/40 mL. Each milliliter contains 5 mg of ipilimumab and the following inactive ingredients: diethylene triamine penta acetic acid (DTPA) (0.04 mg), mannitol (10 mg), polysorbate 80 (vegetable origin) (0.1 mg), sodium chloride (5.85 mg), tris hydrochloride (3.15 mg), and Water for Injection, USP at a pH of 7. 200 mg/40 mL (5 mg/mL). Do not shake product.

Inspect parenteral drug products visually for particulate matter and discoloration prior to administration. Discard vial if solution is cloudy, there is pronounced discoloration (solution may have pale yellow color), or there is foreign particulate matter other than translucent-to white, amorphous particles.

Preparation of Solution:

- Allow the vials to stand at room temperature for approximately 5 minutes prior to preparation of infusion.
- Withdraw the required volume of ipilimumab and transfer into an intravenous bag.
- Dilute with 0.9% Sodium Chloride Injection, USP or 5% Dextrose Injection, USP to prepare a diluted solution with a final concentration ranging from 1 mg/mL to 2 mg/mL. Mix diluted solution by gentle inversion.
- Store the diluted solution for no more than 24 hours under refrigeration (2°C to 8°C, 36°F to 46°F) or at room temperature (20°C to 25°C, 68°F to 77°F).
- Discard partially used vials or empty vials of ipilimumab.

11.2.3 Storage and Stability

Store ipilimumab under refrigeration at 2°C to 8°C (36°F to 46°F). Do not freeze. Protect vials from light.

11.2.4 Administration

Do not mix ipilimumab with, or administer as an infusion with, other medicinal products.

Flush the intravenous line with 0.9% Sodium Chloride Injection, USP or 0.5% Dextrose Injection, USP after each dose.

Administer diluted solution approximately 30 minutes through an intravenous line containing a sterile, non-pyrogenic, low-protein-binding in-line filter.

11.2.5 Handling and Disposal

Accountability for investigational product is the responsibility of the investigator. The research pharmacy will maintain a careful record of the inventory and disposition of the agent using the NCI Drug Accountability Record Form (DARF) or another comparable drug accountability form.

Qualified personnel, familiar with procedures that minimize undue exposure to themselves and the environment, should undertake the preparation, handling, and safe disposal of the chemotherapeutic agent in a self-contained and protective environment.

Drug should be destroyed at the site, after the investigator approves the drug destruction policy at the site. Drug will not be returned to BMS. Destruction will be documented in the Drug Accountability Record Form.

11.2.6 Compatibility

No incompatibilities between the nivolumab and ipilimumab have been observed. When both study drugs are to be administered on the same day, separate infusion bags and filters must be

used for each infusion. Nivolumab is to be administered first. The nivolumab infusion must be promptly followed by a saline flush to clear the line of nivolumab before starting the ipilimumab infusion. The second infusion will always be ipilimumab, and will start at least 30 minutes after completion of the nivolumab infusion.

Ipilimumab may be diluted in 0.9% Sodium Chloride Solution or 5% Dextrose solution. Nivolumab may be diluted in 0.9% Sodium Chloride Solution or 5% Dextrose solution.

Table 5. Summary of Safety with Nivolumab in Combination with Ipilimumab in RCC.

Category Preferred Term	IPI1 + Nivo3 N = 21 n (%)		IPI3 + Nivo1 N = 23 n (%)		Total IPI + Nivo N = 44 n (%)	
	Any Grade	Grade 3-4	Any Grade	Grade 3-4	Any Grade	Grade 3-4
AEs	20 (95.2)	14 (66.7)	23 (100.0)	14 (60.9)	43 (97.7)	28 (63.6)
Drug-related AEs	16 (76.2)	6 (28.6)	23 (100.0)	14 (60.9)	39 (88.6)	20 (45.5)
Drug-related AEs in ≥ 20% of Subjects						
Fatigue	11 (52.4)	0	16 (69.6)	2 (8.7)	27 (61.4)	2 (4.5)
Rash	8 (38.1)	0	4 (17.4)	0	12 (27.3)	0
Diarrhoea	6 (28.6)	1 (4.8)	8 (34.8)	3 (13.0)	14 (31.8)	4 (9.1)
Pruritus	6 (28.6)	0	5 (21.7)	0	11 (25.0)	0
Nausea	4 (19.0)	0	9 (39.1)	0	13 (29.5)	0
Hypothyroidism	3 (14.3)	0	6 (26.1)	0	9 (20.5)	0
Lipase Increased	3 (14.3)	3 (14.3)	6 (26.1)	6 (26.1)	9 (20.5)	9 (20.5)
Decreased Appetite	2 (9.5)	0	6 (26.1)	0	8 (18.2)	0
Vomiting	2 (9.5)	0	6 (26.1)	0	8 (18.2)	0
ALT Increased	1 (4.8)	0	9 (39.1)	6 (26.1)	10 (22.7)	6 (13.6)
Dysgeusia	1 (4.8)	0	5 (21.7)	0	6 (13.6)	0
Weight Decreased	1 (4.8)	0	5 (21.7)	0	6 (13.6)	0
AST Increased	0	0	9 (39.1)	3 (13.0)	9 (20.5)	3 (6.8)
SAEs	9 (42.9)	6 (28.6)	12 (52.2)	9 (39.1)	21 (47.7)	15 (34.1)
Drug-related SAEs in ≥ 5% of Subjects						
Diarrhoea	1 (4.8)	1 (4.8)	2 (8.7)	2 (8.7)	3 (6.8)	3 (6.8)
ALT Increased	0	0	3 (13.0)	3 (13.0)	3 (6.8)	3 (6.8)
AST Increased	0	0	2 (8.7)	2 (8.7)	2 (4.5)	2 (4.5)
AEs Leading to Discontinuation	2 (9.5)	2 (9.5)	6 (26.1)	4 (17.4)	8 (18.2)	6 (13.6)
Drug-related AEs Leading to Discontinuation in ≥ 5% of Subjects						
ALT Increased	0	0	2 (8.7)	1 (4.3)	2 (4.5)	1 (2.3)
Lipase Increased	1 (4.8)	1 (4.8)	2 (8.7)	2 (8.7)	3 (6.8)	3 (6.8)
Deaths	0		3 (13.0)		3 (6.8)	

Source: Preliminary data for CA209016, database lock date 21-Mar-2014

Abbreviations: IPI = ipilimumab; IPI1 = ipilimumab 1 mg/kg; IPI3 = ipilimumab 3 mg/kg; Nivo = nivolumab; Nivo1 = nivolumab 1 mg/kg; Nivo3 = nivolumab 3 mg/kg.

12. ADVERSE EVENTS

Adverse event (AE) monitoring and reporting is a routine part of every clinical trial. The following list of reported and/or potential AEs (Section 12.1) and the characteristics of an observed AE (Section 12.2) will determine whether the event requires expedited reporting **in addition** to routine reporting.

12.1 Adverse Event List for Nivolumab

Based on data from the Phase I study, nivolumab in combination with ipilimumab has an acceptable safety profile in RCC. In summary, AEs were reported in 97.7% of subjects treated with nivolumab in combination with ipilimumab. The most frequently reported drug-related AEs in subjects treated with 3-mg/kg nivolumab + 1-mg/kg ipilimumab included fatigue (11 subjects, 52.4%), rash (8 subjects, 38.1%), diarrhea (6 subjects, 28.6%), and pruritus (6 subjects, 28.6%); the majority were Grade 1-2. The most frequently reported drug-related AEs in subjects treated with 1-mg/kg nivolumab + 3-mg/kg ipilimumab included fatigue (16 subjects, 69.6%); nausea, ALT increased, AST increased (9 subjects each, 39.1%); and diarrhea (8 subjects, 34.8%). The majority were Grade 1-2. The majority of deaths were due to disease progression. No drug-related deaths have been reported to date. See Table 5. Please refer to the most current IB for a comprehensive list of AEs.

12.2 Adverse Event Characteristics

AE term (AE description) and grade: The descriptions and grading scales found in the revised NCI Common Terminology Criteria for Adverse Events (CTCAE) version 4.0 will be utilized for AE reporting. All appropriate treatment areas should have access to a copy of the CTCAE version 4.0. A copy of the CTCAE version 4.0 can be downloaded from the CTEP web site http://ctep.cancer.gov/protocolDevelopment/electronic_applications/ctc.htm.

- **For expedited reporting purposes only:**
 - AEs for the agent(s) that are listed above should be reported only if the adverse event varies in nature, intensity or frequency from the expected toxicity information which is provided.
 - Other AEs for the protocol that do not require expedited reporting are outlined in the next section (Expedited Adverse Event Reporting) under the sub-heading of Protocol-Specific Expedited Adverse Event Reporting Exclusions.

- **Attribution** of the AE:
 - Definite – The AE *is clearly related* to the study treatment.
 - Probable – The AE *is likely related* to the study treatment.
 - Possible – The AE *may be related* to the study treatment.
 - Unlikely – The AE *is doubtfully related* to the study treatment.
 - Unrelated – The AE *is clearly NOT related* to the study treatment.

12.3 DF/HCC and BMS Expedited Adverse Event Reporting

Investigators must report to the Overall PI any serious adverse event (SAE) that occurs after the initial dose of study treatment, during treatment, or within 30 days of the last dose of treatment on the local institutional SAE form. All SAEs that occur following the subject's written consent to participate in the study through 30 days of discontinuation of dosing must be reported to BMS Worldwide Safety using the MedWatch Form 3500A, which can be accessed at <http://www.accessdata.fda.gov/scripts/medwatch/>. The BMS protocol ID number must be included on the MedWatch Form. SAEs, whether related or not related to study drug, and pregnancies must be reported to BMS within 24 hours. SAEs must be recorded on BMS or an approved form; pregnancies must be reported on a Pregnancy Surveillance Form.

SAE Email Address: [REDACTED]

SAE Facsimile Number: [REDACTED]

If only limited information is initially available, follow-up reports are required. (Note: Follow-up SAE reports should include the same investigator term(s) initially reported.)

If an ongoing SAE changes in its intensity or relationship to study drug or if new information becomes available, a follow-up SAE report should be sent within 24 hours to BMS (or designee) using the same procedure used for transmitting the initial SAE report.

All SAEs should be followed to resolution or stabilization.

The Sponsor will reconcile the clinical database SAE cases transmitted from BMS Global Pharmacovigilance (GPV&E) on a quarterly basis. BMS GPV&E will email, upon request from the Investigator, the GPV&E reconciliation report. Requests for reconciliation should be sent to [REDACTED]. The data elements listed on the GPV&E reconciliation report will be used for case identification purposes. If the Investigator determines a case was not transmitted to BMS GPV&E, the case should be sent immediately to BMS.

For multi-institution studies where a DF/HCC investigator is serving as the Overall Principal Investigator, each participating institution must abide by the reporting requirements set by the DF/HCC. This applies to any medical event equivalent to an unexpected grade 2 or 3 with a possible, probable or definite attribution, grade 4 toxicities, and grade 5 (death) regardless of study phase or attribution.

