5. SUBJECT REGISTRATION

5.1 General Guidelines for DF/HCC Institutions

Institutions will register eligible participants in the Clinical Trials Management System (CTMS) OnCore. Registrations must occur prior to the initiation of protocol therapy. Any participant not registered to the protocol before protocol therapy begins will be considered ineligible and registration will be denied.

An investigator will confirm eligibility criteria and a member of the study team will complete the protocol-specific eligibility checklist.

Following registration, participants will undergo a mandatory fresh tumor biopsy prior to starting protocol therapy. Issues that would cause treatment delays should be discussed with the Overall Principal Investigator (PI). If a participant does not receive protocol therapy following registration, the participant's registration on the study must be canceled. Registration cancellations must be made in OnCore as soon as possible.

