6.9 Replacement

A subject who discontinues study participation prematurely for any reason is defined as a “dropout” if the subject has already been assigned to treatment or administered at least one dose of the study drug. Subjects who have dropped out but have not received at least one dose of treatment will be replaced. Subjects who have not received at least one dose of treatment will not be included in data analysis and thus will not require data entry.

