13.7.2 Secondary Analysis

PFS and OS: The progression-free survival (PFS), and overall survival (OS) will each be summarized using the product-limit method of Kaplan-Meier. Median times for each endpoint will be presented with two-sided 90% confidence intervals estimated using log(-log(survival)) methodology. Kaplan-Meier estimates of PFS at 6 or 12 months may also be presented with two-sided 90% confidence intervals.

Salvage Therapy-Free Interval: The proportion of subjects re-start nivolumab since nivolumab discontinuation (arm A) during 1-year will be estimated with two-sided 90% confidence intervals. In addition, the reasons for re-starting nivolumab (Arm A) will be tabulated.

Subset analysis of study endpoints will be explored according to IMDC* risk group (favorable, intermediate, versus poor risk); prior systemic treatment for RCC (yes versus no); first line versus second line targeted therapy; histology (clear cell versus non-clear cell RCC subtypes; sarcomatoid components present versus absent)

*IMDC risk factors include ECOG < 1, time from original diagnosis to treatment less than one year, hemoglobin less than the lower limit of normal, and serum calcium, neutrophil count, or platelet count greater than the upper limit of normal

Immune Related Objective Response Rate: The proportion of subjects with immune ORR will be presented with two-sided 90% confidence interval estimated using exact binomial methods.

Safety and Tolerability: All adverse events recorded during the trial will be summarized for the safety population. The incidence of events that are new or worsening from the time of first dose of treatment will be summarized according to system organ class and/or preferred term, severity (based on CTCAE version 4), type of adverse event, and relation to study treatment.

The worst grade will be used if any toxicity event is reported multiple times on the same participant. All adverse events resulting in discontinuation, and/or dosing interruption, and/or treatment delay will also be summarized.

Given the potential multiple treatment sequences, the incidence of events (grade 3+) will be summarized according to treatment arms as well as the type of therapies they are on at the time of events.

Deaths reportable as SAEs and non-fatal serious adverse events will be listed by patient and tabulated by primary system organ class, and type of adverse event.

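### Section 12.3 opens the Overall PI's SAE window at first dose but BMS's at consent, so SAEs from the mandatory pre-dose biopsy miss the Overall PI's rule and, in subjects never dosed, the safety tables

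*Combined protocol and SAP*

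**What the plan says.** **Reporting windows (12.3).** For the Overall PI the rule is "Investigators must report to the Overall PI any serious adverse event (SAE) that occurs after the initial dose of study treatment", and it closes 30 days after the last dose. For BMS the rule is "All SAEs that occur following the subject's written consent to participate in the study through 30 days of discontinuation of dosing must be reported", and on scope and deadline: "SAEs, whether related or not related to study drug, and pregnancies must be reported to BMS within 24 hours". Section 12.4 makes the Overall PI, as sponsor, responsible for reporting to the FDA.

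**Timing of the biopsy.** Section 5.1: "Following registration, participants will undergo a mandatory fresh tumor biopsy prior to starting protocol therapy". Footnote 10 of the primary treatment calendar (Section 8) says the same and gives correlative work as the purpose.

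**Subjects never dosed.** Sections 5.1 and 5.3 require the registration to be canceled. Section 6.9 replaces such subjects and says they "will not be included in data analysis and thus will not require data entry".

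**Safety analysis.** The safety population in 13.4 needs at least one dose of either drug. Section 13.7.2: "The incidence of events that are new or worsening from the time of first dose of treatment will be summarized".

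**Attribution and the DF/HCC table.** The five-level scale in 12.2 refers only to study treatment. The table in 12.3.1 asks for no report of a Grade 2-3 event rated unrelated or unlikely.

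**Later biopsy.** The single-cell cohort (25 subjects) has a second mandatory biopsy when treatment ends for good or the subject goes off study. The Arm A and Arm B calendars mark it in the end-of-treatment column, a visit set at 30 days (+/- 7) after the last dose.

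**The concern.** The baseline biopsy is required by the protocol for research, so its complications are harms of taking part. The interval in which they would first appear, from biopsy to first dose, is the interval that the Overall PI's SAE rule omits and the BMS rule includes. The party that answers to the FDA therefore has the narrower rule, in the same paragraph as the wider one.

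The second problem is selection on outcome. A subject whose complication rules out dosing is canceled, replaced and excused from data entry. One with a milder complication goes on to be dosed and has a case report form (CRF). Any account of biopsy safety drawn from the database would therefore lack the complications that stopped treatment.

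**Working it through.** The plan states no figure to reproduce, and the point turns on which rules apply. Take one case: a Grade 3 bleed after the baseline biopsy and before the first dose, with more than 24 hours in hospital. That is an SAE under 12.3.2. Suppose the investigator scores it unrelated to study treatment, which is natural because no drug has been given and 12.2 offers no category for a procedure.

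| Route | Does it capture the case? |
|---|---|
| Overall PI SAE rule (12.3) | No: it opens after the first dose |
| BMS (12.3) | Yes: from consent, related or not, within 24 hours |
| DF/HCC table (12.3.1) | No: Grade 2-3, unrelated, no report required |
| Life-threatening rule (Appendix D, 3.9) | No, unless the bleed is life-threatening |
| SAEs to the Coordinating Center (Appendix D, 3.9) | Refers back to the protocol, hence to Section 12 |
| CRF (12.6; calendar marks AEs at screening) | Yes if later dosed; data entry waived by 6.9 if never dosed |
| Safety tables (13.4, 13.7.2) | Never dosed: absent. Dosed: outside the incidence count from first dose unless the event worsens |

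So BMS is the only stated expedited recipient.

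Now raise the grade. A Grade 4 event is reportable within 5 calendar days and a Grade 5 event within 24 hours, whatever the attribution. For Grade 4 the table exempts an event that the protocol lists as expected and not needing expedited reporting. DF/HCC sites send these to the DFCI Office for Human Research Studies; a copy to the Overall PI is stated only for other sites.

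Two conflicts follow for never-dosed subjects:

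- 12.6 wants every adverse event on a CRF sent to the Overall PI; 6.9 requires no data entry.
- The Evaluable set in 13.4 includes subjects who die before being evaluated at all; 6.9 removes anyone never dosed from the analysis.

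**End-of-treatment biopsy.** The visit falls between day 30 - 7 = 23 and day 30 + 7 = 37 after the last dose. Both SAE windows close at day 30. A biopsy on day 23 has 30 - 23 = 7 days of cover, one on day 30 has none, and one on day 37 comes 37 - 30 = 7 days after both windows have closed.

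**Number exposed.** The 83 baseline biopsies are a ceiling. Section 6 allows omission when the procedure is judged medically unsafe, and footnote 10 and 9.3.2 accept tissue from a procedure within the preceding 12 months. The 25 second biopsies are also a ceiling, since the calendars ask for them only when safe and feasible.

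**The case against.** The strongest reply is that serious harms are already covered. SAEs go to BMS from consent and are followed to resolution or stabilization, with quarterly reconciliation against the clinical database. Grade 4-5 and life-threatening events have their own routes. All of this stands. It rules out the reading, which a reader might infer, that the worst biopsy harms vanish from the trial record. For expedited reporting the least covered group is non-serious Grade 2-3 events rated unrelated, not the gravest. Reconciliation closes the gap only partly: it is quarterly, and a canceled subject may have no database record to match.

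A second reply is that a dosed-only safety set fits the objective in 3.1.2, which concerns safety in Arms A and B, and that no objective covers biopsy risk. That is fair, and the safety population need not change. It does not explain two SAE start points in one paragraph, or 6.9 against 12.6 and 13.4.

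Three further readings are tempting and unsupported:

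- That the sponsor and the monitoring committee would see no biopsy signal. They have the routes above, and 14.2 allows the committee reported unexpected events of Grade 2 or higher and deaths within 30 days of intervention. They may not see one reliably; more cannot be said.
- That the second biopsy may come more than a year after the last dose for an Arm A subject under observation. The calendar ties it to the end-of-treatment visit, and progression in observation restarts nivolumab, which resets the last dose. The off-study criteria in 6.8 are loss to follow-up, withdrawal of consent and death.
- That the loss can be quantified. An assumed serious complication rate of 1% to 5% gives 83 x 0.01 = 0.83 to 83 x 0.05 = 4.15 expected events, and a chance of at least one of 1 - 0.99^83 = 57% to 1 - 0.95^83 = 99%. That rate is not in the documents, 83 is a maximum, and the result counts any serious complication, not one that prevents dosing.

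**Conclusion.** The point holds as a reporting and data-capture gap. Under the rules as written, a pre-dose biopsy SAE is outside the Overall PI's SAE rule. At Grade 2-3 and scored unrelated, it has BMS as its only stated expedited recipient. If it prevents dosing, it also loses CRF capture and its place in the safety summary. Complications of the single-cell cohort's end-of-treatment biopsy can fall after both 30-day windows.

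The size cannot be estimated: the plan gives neither a complication rate nor the share of complications that would prevent dosing. The conclusion rests on the text alone, plus one assumption, that a biopsy complication would be scored unrelated on a scale that names only study treatment. It merits correction because it concerns notice of harm to the sponsor, but it does not touch the primary endpoints.

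**What to change.** 1. In 12.3, start the Overall PI's SAE window at written consent, as for BMS, and extend SAE reporting to a stated period after any protocol-mandated biopsy, including the end-of-treatment one.
2. In 6.9, require adverse event data entry for registered subjects who had a protocol biopsy but were never dosed. Reconcile that section with 12.6 and with the Evaluable set in 13.4. In 13.7.2, list biopsy complications over all biopsied subjects, separately from the dosed safety population, which stays as it is.
3. In 12.2, let attribution record relation to a study procedure.

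The cost is wording in these sections, a few adverse event pages for canceled subjects and one CRF field. Sites already owe BMS the pre-dose SAEs, so little new reporting is created.
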